2.1 Primary Objectives

Period 1 (dose escalation = short-term outcomes; 6-weeks) and Period 2 (follow-up = longer-term outcomes; 12-weeks)

Short-term and longer-term efficacy: To test the hypothesis that furosemide will increase 24-hour urine volume at its maximally tolerated dose in individuals with HD-dependent ESKD. 24-hour urine volumes will be used as the primary endpoint for both short-term and longer-term efficacy assessments.

Short-term and longer-term safety: To evaluate the short-term (6-weeks) and longer-term (12-weeks) safety of escalating doses of furosemide in individuals with HD-dependent ESKD. Safety outcomes will include the following:

- Serum potassium level <3.2 mEq/L
- Serum magnesium level <0.8 mg/dL
- Serum corrected calcium level <7 mg/dL
- Serum furosemide level >12 microgram/L
- Serious dialysis-associated hypotension defined as hypotension requiring hospitalization or treatment in an emergency room and not attributable to overt sepsis, acute myocardial infarction, or other cardiovascular event (e.g. aortic dissection)
- Severe or very severe rash, tinnitus, or hearing change not attributable to causes other than furosemide
- Inner EAR score decrease by ≥10 points

Short-term and longer-term tolerability: To evaluate the short-term and longer-term tolerability of furosemide in individuals with HD-dependent ESKD. Tolerability will be assessed by:

• Severe or very severe cramping, dizziness/pre-syncope, unusual tiredness/weakness, chest pain, nausea, vomiting, or diarrhea not attributable to causes other than furosemide

Short-term and longer-term acceptability: To evaluate the short-term and longer-term acceptability of furosemide in individuals with HD-dependent ESKD. Acceptability will be assessed by:

- Participant affirmative response to question: "If recommended, would you be willing to stay on the dose of furosemide you have received during the last week?"
- Recruitment rates
- Drop-out rates

Short-term adherence: To evaluate short-term and longer-term adherence to furosemide among individuals with HDdependent ESKD. Adherence will be assessed by:

- Pill counts
- Serum and urine furosemide levels

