4.4 Follow- up procedures (by visit types)

All study visits will occur at the time of routinely scheduled HD treatments at the patient's usual outpatient dialysis clinic. *Section 5* describes the measurements and assessments in detail.

Blood samples (weeks 1, 2, 3, 4, 5, 6, 10, 14, and 18): Blood will be obtained for the measurement of serum sodium, potassium, chloride, urea, creatinine, magnesium, calcium, albumin, and furosemide level. An additional 2.5 mL blood sample will be drawn, frozen, and stored in UNC Kidney Center -80° freezers for future testing as needed.

Urine samples (weeks -1, 5, 12, and 18): 24-hour urine collections will be obtained for the measurement of urine volume, sodium, urea, creatinine, and furosemide level. An aliquot of urine will be taken from the sample after the before-listed measurements are performed and be frozen and stored in UNC Kidney Center -80° freezers for future testing as needed.

Adherence assessments (weeks 1, 2, 3, 4, 5, 6, 8, 10, 12, 14, 16, and 18): Study staff will complete pill counts.

Acceptance assessments (weeks 1, 2, 3, 4, 5, 6, 8, 10, 12, 14, 16, and 18): Study staff will ask the participant the acceptance question.

Symptom assessments (weeks 1, 2, 3, 4, 5, 6, 8, 10, 12, 14, 16, and 18): Study staff will administer surveys evaluating patient-reported cramping, dizziness/pre-syncope, unusual tiredness/weakness, chest pain, rash, nausea, vomiting, diarrhea, tinnitus, hearing change, and numbness/tingling.

Hearing assessments (weeks 2, 4, 6, 10, 14, and 18): Study staff will administer the Inner EAR instrument.

Clinical data (weeks -4 to 18): HD treatment-level data (BPs, weights, dialysis prescription) will be obtained from the EHR.

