Serum blood tests: The following tests will be assessed via blood samples: sodium, potassium, chloride, urea, creatinine, magnesium, calcium, albumin and serum furosemide level. An additional 2.5 mL blood sample will be drawn, frozen, and stored in UNC Kidney Center -80° freezers for future testing as needed. Blood samples will be collected via the vascular access by trained dialysis clinic personnel.

24-hour urine collection: The following tests will be assessed via 24-hour urine collections: urine volume, sodium, urea, creatinine, and urine furosemide level. An aliquot of urine will be taken from the sample after the before-listed measurements are performed and be frozen and stored in UNC Kidney Center -80° freezers for future testing as needed. Urine samples will be collected by the patient in 24-hour urine collection containers. Containers will be provided by and returned to study staff at the dialysis clinic at specified study visits.

Symptom assessment: Study staff will administer a symptom questionnaire (*Appendix, Section 13.1*) to participants at specified study visits.

Hearing assessment: Study staff will administer the Inner Ear instrument (*Appendix, Section 13.2*) to participants at specified study visits.

Pill counts: Study staff will perform pill counts at specified study visits.

Acceptance assessment: Study staff will ask participants the following yes/no/unsure question: "If recommended, would you be willing to stay on the dose of furosemide you have received during the last week?"

Clinical data: The following data will be obtained from the EHR: HD treatment BPs (systolic and diastolic), weights (preand post-HD), UF volumes/rates, dialysate composition (sodium, potassium, bicarbonate, calcium), dialysate and blood flow rates, and vascular access type.

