6.1 Primary Endpoints

Short-term and longer-term efficacy- urine volume (assessed separately)

- Among participants with baseline 24-hour urine volume ≥200 mL: incidence of ≥25% increase in urine volume
- Among participants with baseline 24-hour urine volume <200 mL: incidence of a ≥50 mL increase in urine volume to a urine volume of at least 100 mL/24-hours

Short-term and longer-term safety- electrolytes (assessed separately)

- Incidence of serum potassium <3.2 mEq/L
- Incidence of serum magnesium <0.8 mg/dL
- Incidence of serum corrected calcium <7.0 mg/dL

Short-term and longer-term safety- furosemide levels

• Incidence of serum furosemide level >12 microgram/L

Short-term and longer-term safety- BP

 Incidence of dialysis-associated hypotension requiring hospitalization or treatment in an emergency room and not attributable to overt sepsis, acute myocardial infarction, or other cardiovascular event (e.g. aortic dissection)²¹

Short-term and longer-term safety- symptoms (assessed separately)

- Incidence of severe or very severe patient-reported rash, tinnitus, or hearing change) not attributable to causes
 other than furosemide
- Incidence of 10-point decrease in Inner EAR instrument score

Short-term and longer-term tolerability- symptoms (assessed separately)

• Incidence of severe or very severe patient-reported cramping, dizziness/pre-syncope, unusual tiredness/weakness, chest pain, nausea, vomiting, or diarrhea not attributable to causes other than furosemide

Short-term and longer-term acceptability

• Incidence of an affirmative response to the furosemide acceptance question

Short term- and longer-term adherence

• Incidence of participants having <20% of furosemide pills remaining at pill counts

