6.2 Exploratory Endpoints

Short-term and longer-term efficacy- alternative definitions (assessed separately)

- Absolute change in urine volume from baseline (continuous in mL urine)
- Percentage change in urine volume from baseline (continuous in %)

Short-term and longer-term safety- electrolytes- alternative definitions (assessed separately)

- Absolute change in serum potassium from baseline (continuous in mEq/L)
- Absolute change in serum magnesium from baseline (continuous in mg/dL)
- Absolute change in serum corrected calcium from baseline (continuous in mg/dL)
- Percentage change in serum potassium from baseline (continuous in %)
- Percentage change in serum magnesium from baseline (continuous in %)
- Percentage change in serum corrected calcium from baseline (continuous in %)

Short-term and longer-term safety- BP- alternative definitions (assessed separately)

- Incidence of intradialytic systolic BP <80 mmHg²¹
- Incidence of intradialytic systolic BP <90 mmHg⁴¹
- Lowest systolic BP during HD (continuous in mmHg)

Short-term and longer-term acceptability alternative definitions (assessed separately)

- Number (percentage) of participants withdrawing from the study
- Number (percentage) period 1 participants not continuing to period 2

Short-term and longer-term adherence alternative definitions (assessed separately)

- Number (percentage) of furosemide tablets not taken (# tablets remaining/# tablets provided)
- Serum furosemide level (continuous in microgram/L and binary, present vs. absent)
- Urine furosemide level (continuous in microgram/L and binary, present vs. absent)

Clinical endpoints (assessed separately)

- Change in 24-hour creatinine clearance from baseline (continuous in ml/min/1.73m²)
- Percentage change in 24-hour creatinine clearance from baseline (continuous in %)
- Change in 24-hour fractional excretion of sodium from baseline (continuous in %)

- Change in 24-hour fractional excretion of urea from baseline (continuous in %)
- Percentage change in 24-hour fractional excretion of urea from baseline (continuous in %)
- Pre-HD systolic BP (mmHg on a per-HD treatment basis)
- IDWG (kg on a per-HD treatment basis)
- UF volume (mL on a per-HD treatment basis)
- UF rate (mL/h/kg on a per-HD treatment basis)
- Target weight achievement (post-HD weight (kg) within 1kg of prescribed target weight) (binary on a per-HD treatment basis)

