6.3.4 Primary analyses (each assessed separately)

At designated study time-points, we will determine the [data type; see **Section 6.1** for definitions]:

- change from baseline for the short and longer-term efficacy measure [binary] (24-hour urine volume);
- value of short and longer-term safety electrolyte measures [binary] (serum potassium, magnesium, corrected calcium);

- value of serum furosemide levels [binary] (short and longer-term safety furosemide level measure);
- incidence of dialysis-associated hypotension [binary] (short and longer-term safety blood pressure);
- incidence of severe or very severe patient-reported allergic or toxicity-related symptoms [binary] (short and longer-term safety symptom measures);
- change from baseline of Inner EAR instrument score [binary] (short and longer-term safety symptom measure);
- incidence of severe or very severe patient reported symptoms [binary] (short and longer-term tolerability symptom measures);
- incidence of patient-reported acceptance of furosemide [binary] (short and longer-term acceptability measure);
- incidence of adherence by pill counts [binary] (short and longer-term adherence measure).

Change measures and value measures (e.g. 24-hour urine volume, serum electrolytes, serum furosemide level) will be analyzed via one-way repeated measures of analysis of variance to determine the presence of absence of dose-related differences. In addition, we will use mixed effects modeling to test the effect of increased dose and duration with the fixed effect of time (dose), random subject effect, and an unstructured repeated covariance type. We will use generalized estimating equations to assess categorical outcomes (e.g. sufficient increase in 24-h urine volume, hypokalemia, hypomagnesemia, hypotension, symptoms, Inner EAR score, patient acceptance). We will also consider binary outcomes as rates (events/time).

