13 APPENDICES

13.1 Symptom Assessment

Items

During your dialysis treatments over the [last week (for dose titration period) and two weeks (for follow-up period)] did you have...?

- 1. Cramping
- 2. Dizziness or lightheadedness
- 3. Unusual tiredness
- 4. Unusual weakness
- 5. Chest pain
- 6. New rash
- 7. Nausea
- 8. Vomiting
- 9. Diarrhea
- 10. Tinnitus or ear ringing
- 11. Hearing change
- 12. Other (patient self-report)

Response Options: 0=did not have.

• If present, how severe was it? 1=mild, 2=moderate, 3=severe, 4=very severe

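### The symptom form asks only about dialysis treatments but the primary symptom endpoints have no such limit, so a literal reading can under-count tolerability symptoms between sessions

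*Combined protocol and SAP*

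**What the plan says.** The appendix form (Section 13.1) opens with "During your dialysis treatments over the [last week (for dose titration period) and two weeks (for follow-up period)] did you have", followed by 12 items, the last being a free self-report. An absent symptom scores 0. A symptom that is present is graded from 1 (mild) to 4 (very severe).

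The objectives and endpoints read differently. Section 2.1 assesses tolerability by "Severe or very severe cramping, dizziness/pre-syncope, unusual tiredness/weakness, chest pain, nausea, vomiting, or diarrhea not attributable to causes other than furosemide". Section 6.1 turns this into a primary endpoint that begins "Incidence of severe or very severe patient-reported cramping, dizziness/pre-syncope", and Section 6.3.4 carries it into the primary analyses as a binary measure. The primary safety symptom endpoint (rash, tinnitus, hearing change) is worded in the same way. Both endpoints are qualified by severity and attribution only. Neither says when or where the symptom must occur.

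The procedural sections add no session limit either. Section 4.4 states "Study staff will administer surveys evaluating patient-reported cramping, dizziness/pre-syncope, unusual tiredness/weakness, chest pain, rash, nausea, vomiting, diarrhea, tinnitus, hearing change, and numbness/tingling". Section 5.1 states "Study staff will administer a symptom questionnaire" and refers the reader to Section 13.1 for it.

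**The concern.** The instrument and the endpoint describe different time frames. The endpoint reads as symptoms on treatment. The form, taken literally, collects symptoms during dialysis. The drug is an oral medicine dispensed in 2-week and 4-week supplies (Section 3.5.3), so exposure is not confined to sessions.

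Tolerability is a primary endpoint, Section 7.5 names safety and tolerability as the main focus of the pilot, and Section 6.4 intends the results to support a later randomized trial. An incidence that leaves out events at home would make furosemide look better tolerated than it was. If some staff and participants keep to the stem while others answer for the whole week, the recorded incidence has no single meaning. A severity grade that was not asked for at the visit may also be hard to recover afterwards.

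**Working it through.** The plan states no figure on this point, so there is none to reproduce. The check compares the texts and counts the scope.

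1. **Items under the stem (Section 13.1).** Items 1, 2, 3, 4, 5, 7, 8 and 9 match the tolerability endpoint. That is 8 items for 7 named symptoms, because tiredness and weakness are asked separately. Items 6, 10 and 11 (rash, tinnitus, hearing change) match the safety symptom endpoint, which is 3 items. Item 12 is the free self-report. Total: 8 + 3 + 1 = 12, so every item falls under the dialysis stem.

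2. **Number of administrations (Section 4.4).** Weeks 1, 2, 3, 4, 5, 6, 8, 10, 12, 14, 16 and 18 give 12 post-baseline assessments. The form is also given at baseline in week -1.

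3. **Path from answer to endpoint.** Take a participant with severe vomiting at home and none during sessions. The literal answer to the stem is that the symptom did not occur, which scores 0. The severity question is put only when a symptom is present, so this episode cannot reach grade 3 or 4, and those are the grades the endpoint requires.

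4. **Whether the form feeds the endpoint.** Sections 6.1 and 6.3.4 name no data source. That the form supplies the data is an inference from three facts: Section 5.1 makes it the scheduled symptom measure, Section 7.1.5 relies on the symptom assessment for self-reported hearing change, and the endpoint's severity terms are the form's top two grades.

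5. **Other route for the same event.** Section 7.3 requires AE questioning at each contact, with no session limit, recorded in the source document and on the AE log. Under Section 7.1.1 a between-session episode is an AE. None of the tolerability symptoms is among the 12 events that Section 7.3.2 removes from ordinary AE recording below a threshold. The episode may therefore be logged. No section says that logged symptoms count toward the 6.1 endpoints, and none says that they do not.

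6. **Which symptoms are exposed.** Episodic ones: vomiting, diarrhea, nausea, cramping, dizziness. Rash, tinnitus and hearing change can persist into a session. Section 7.3.2 sets AE reporting triggers for them without a session limit, and hearing is also followed with the Inner EAR score.

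7. **Direction and size.** Events missed in this way only lower the count, so the bias is downward. Its size depends on when symptoms occur, how literally the stem is applied, and whether AE-log symptoms are counted. The documents give none of these.

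**The case against.** The strongest reply is that the loss may be small or absent. AE questioning has no session limit and could find the same events. Staff administer the form, and items such as rash, diarrhea and hearing change fit a within-session question badly, so people may well answer for the whole week. Other information without a session limit also bears on tolerability: the acceptance question at the same 12 visits, withdrawals, non-continuation to period 2, and the titration-ending events in Section 1.3.1. The same form is used at baseline, so comparisons over time share one frame.

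Much of this stands, and it makes the bias conditional. It does not remove the mismatch. An AE entry does not change the form score, the other measures do not supply the 6.1 symptom count, and a shared frame at baseline still leaves the endpoint describing symptoms on dialysis. Section 1.3.2 does hypothesise a benefit on symptoms during dialysis. If the stem was chosen for that reason, Sections 2.1 and 6.1 need to say so.

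Three stronger readings are tempting, and the documents do not support them:

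- A reader might infer that the symptom endpoints omit a dialysis limit on purpose, because the blood pressure endpoints state one ("Incidence of dialysis-associated hypotension requiring hospitalization or treatment in an emergency room"; "Incidence of intradialytic systolic BP <80 mmHg"). But the protocol uses such qualifiers unevenly. The systolic BP <80 mmHg titration rule is intradialytic in Sections 1.2, 3.5.2 and 4.3 but has no such word in Section 1.3.1. Omission therefore says little about intent.
- A reader might infer that AE symptoms cannot be graded, because no AE severity scale appears. The AE forms are not part of the documents, and Section 7.6.2 has the external monitor review AE severity.
- A reader might use the share of the week spent on dialysis as the size of the loss. Session length is not given. At an assumed 3 to 5 hours, three sessions cover 9 to 15 of 168 hours (9/168 = 5.4%; 15/168 = 8.9%). That is time covered, not symptoms captured, and cramping or dizziness may cluster in sessions.

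**Conclusion.** The concern holds as a mismatch between a primary endpoint and its scheduled instrument, and it should be reconciled. Confidence in the mismatch is high, because it rests on the wording alone. Confidence in the downward bias is moderate. It rests on two assumptions: that the stem is applied literally, and that symptoms known only from AE questioning are left out of the 6.1 count. If both hold, the tolerability incidence is too low by an unknown amount. If the stem is applied unevenly, the answers are not comparable between participants or visits. The documents do not show that between-session symptoms will in fact be lost.

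**What to change.** **Preferred.** Reword the 13.1 stem to cover the whole interval, for example: *At any time over the last week [two weeks], at home or during dialysis, did you have...?* An optional tick-box for occurrence during dialysis would keep the Section 1.3.2 question answerable. Add to Section 6.1 a statement of whether symptoms found only through AE questioning count toward the symptom endpoints and, if so, that they are graded on the 13.1 scale.

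**Alternative.** Keep the stem, and restate the symptom endpoints in Sections 2.1 and 6.1, and the conclusions drawn from them, as symptoms during dialysis treatments.

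**Cost.** The preferred option needs a form amendment with IRB approval. It will record more background symptoms, which the attribution wording in Section 6.1 must then handle. If enrolment has begun, the form version must be recorded and results shown by version. The alternative is a change of text only, at the price of a narrower tolerability claim.

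**Separate minor point.** Numbness/tingling is part of the survey in Section 4.4 but has no item of its own in Section 13.1. It can be settled in the same amendment.

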13.2 Inner EAR Instrument

Items

- 1. Ability to understand with a family and close friends are saying.
- 2. Ability to understand speech in a quiet room.
- 3. Ability to hear what is said by those at your table in a crowded restaurant.
- 4. Ability to hear what you want and filter out unwanted noises.
- 5. Ability to hear telephone conversations.
- 6. Ability to hear in different listening situations.
- 7. Ability to hear soft household sounds (e.g. car turn signal, clock ticking).
- 8. Mood based on your ability to hear.
- 9. Bothered by having to ask people to repeat.
- 10. Bothered by having to restrict activities because of your hearing.
- 11. Please rate your overall hearing.

Response Options

Questions 1-8: 5-point Likert scale- 1=poor, 2=fair, 3=good, 4=very good, 5=excellent

Questions 9-10: 4-point Likert scale- 1=very bothered, 2=somewhat bothered, 3=a little bothered, 4=not bothered

Question 11: 11-point scale (select a number between 0 and 11 with the following markers- 0=hate, 5=it's OK, 10=love it
